5.1 Description

CONFIDENTIAL

Imiquimod is a topical immunomodulator approved for the treatment of actinic keratosis, superficial basal cell carcinoma, and external genital and perianal warts (condylomata acuminata) from human papilloma virus (HPV) infection. Each gram of 5% Imiquimod cream contains 50 mg of Imiquimod in an off-white oil-in-water vanishing cream base consisting of isostearic acid, cetyl alcohol, stearyl alcohol, white petrolatum, polysorbate 60, sorbitan monostearate, glycerin, xanthan gum, purified water, benzyl alcohol, methylparaben, and propylparaben (7).

5% Imiquimod is supplied in single-use packets each of which contains 250mg of the cream, equivalent to 12.5mg of Imiquimod. It is supplied in a box of 24 packets each (7).

5.2 Treatment Regimen

Topical dosage (5% cream)

Apply a thin coat of Imiquimod cream to cover the entire lesion once daily 5-times per week prior to normal sleeping hours, for 6 weeks, starting 1 week prior to keloid excision. Cream should be left in place for approximately 8 hours. The target keloid should have a maximum diameter of no more than 5cm and be located on the trunk (excluding anogenital skin), below the neck, or extremities (excluding hands or feet). The treatment area should include a 1 cm margin of skin around the tumor. The diameter of cream droplet applied should range from 5 mm to 10 mm for keloid areas of 0.5 cm to 5 cm, respectively. Subjects should wash hands thoroughly prior to and after application of medication. Maximum to be prescribed: 36 packets during the 6-week treatment period.

A rest period of several days during treatment may be required due to local skin reactions. Follow-up visits will be scheduled at 2, 4, and 8 weeks after excision and as needed for local skin reactions.

The following dosing algorithm will be used at the 2 and 4 visits and unscheduled visits due to local toxicity to adjust the frequency of application accordingly.

- If intolerable at 5 days per week; stop completely for 1 week then restart but at a reduced dose of 3 days per week. Increase to 5 days per week as soon as tolerable.
- If intolerable at 3 days per week, a further week off, start again at 3 days per week. Stop if intolerable.

Subjects will be requested to contact the local investigator for advice before stopping or changing treatment.

5.3 Method for Assigning Subjects to Treatment Groups

This is a single-arm study. All patients will be receiving open-label active drug.

5.4 Preparation and Administration of Study Drug

The principle investigator or dermatology physician designated by the PI will prescribe the 5% Imiquimod cream for the patient. Study medication will consist of the number of packets as ordered by the PI necessary to treat the Keloid. The study drug will be purchased with start-up funds from the PI, and it will be provided to the patient free of charge. Study medication will be open label (see section for study drug details).

5.5 Subject Compliance Monitoring

Compliance with study procedures will be monitored throughout the trial. It is expected that the Investigator will comply with the protocol requirements and encourage subjects to follow all procedures carefully. Subject compliance with treatment administration will be calculated as the percentage of the reported number of doses administered compared to the number that should have been administered while the subject is on study. The total number of packets utilized will be compared to the total number prescribed. Additionally, application site will be evaluated for erythema and local site reaction.

CONFIDENTIAL

5.6 Prior and Concomitant Therapy

Concomitant medications/treatment for the keloid lesions should be kept to a minimum during the study. However, if considered necessary for the subject's welfare they may be given at the discretion of the investigator according to the local standard of care. The drug, dose and duration should be recorded.

Immunosuppressive medications including oral corticosteroids are specifically excluded for the duration of this study. A reconciliation of recorded medications in the electronic medical system will be performed at the screening visit.

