1.1 Background

Keloids are benign dermal fibroproliferative tumors that represent a form of abnormal wound healing following any insult to the deep dermis, including lacerations, abrasions, surgery, piercings, vaccinations, and burns in predisposed individuals (1). They are distinguished from hypertrophic scars, another type of abnormal scar formation, by their extension beyond the borders of the original wound, failure to regress spontaneously, and tendency to recur following excision (1).

Keloids tend to occur more frequently in dark-skinned individuals, with an incidence of up to 16% in those of black and Hispanic backgrounds (2). These lesions appear to affect male and female subjects equally and most commonly occur in persons aged 10-30 years (2). They typically form on the ears, face, chest, and shoulders and can cause pain, burning, itching, and restriction of motion. Furthermore, the scars can be extremely disfiguring and potentially cause significant social and psychological distress in affected individuals.

The process by which keloids develop is poorly understood, though most theories of keloid etiology relate to fibroblast dysfunction (2). These lesions are difficult to treat, as they frequently recur following excisional removal. Current treatment options include surgical excision, laser, intralesional injections, pressure and silicone dressings, topical preparations, oral agents, radiation, and cryotherapy (1). Oftentimes, surgical excision is combined with adjuvant therapies such as corticosteroids and immunomodulators at the time of skin closure because surgical excision alone has recurrence rates ranging between 45% and 100% (3). Additionally, because surgical excision requires complete removal of all abnormal tissue, post-excision keloid recurrence may lead to a larger keloid than prior to excision. Although many adjuvant therapies to surgical excision and modalities for keloid removal have been proposed, there has been no consensus regarding how to best treat these lesions, and there is currently no medication approved for the indication of reducing keloid recurrence after excision.

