Because the effects of the drug are not well studied in pregnancy and during breastfeeding, it is possible that there are harmful side effects that are not yet known to both the mother and unborn or breast-feeding child. Therefore, pregnant and breastfeeding subjects are excluded from the study. Additionally, the risks of this study includes risks of breach of confidentiality. While every effort will be made to protect the confidentiality of study subjects, there is a potential risk of an inadvertent or unintended breach of confidentiality.

As demonstrated in patients who have used 5% Imiquimod for other FDA approved indications, risks of topical application of 5% imiquimod are minimal. Additionally, previous studies as well as our preclinical data indicates that 5% imiquimod could modulate wound healing and prevent keloid recurrence in patients when applied prior to keloid-excision and continued after the procedure. Therefore, we believe that the benefit of possible decrease in keloid recurrence outweighs the minimal risks posed by topical 5% imiquimod therapy.

2 Study Objectives

Primary Objective

To assess the efficacy of 5% Imiquimod cream on preventing keloid recurrence after excision. Subjects will be evaluated by a consultant dermatologist at 2, 4, and 8 weeks following excision and by phone 12 weeks after excision to assess for clinical evidence of lesion recurrence.

[figure not shown]
Secondary Objectives

To assess the safety and tolerability of 5% Imiquimod in subjects undergoing keloid excision. Subjects will be evaluated by a consultant dermatologist at 2, 4, and 8 weeks following excision to assess for local site reaction such as redness, discomfort, swelling, and ulceration.

3 Study Design

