4.4 Early Withdrawal of Subjects

4.4.1 When and How to Withdraw Subjects

The participant will stop Imiquimod treatment early for the following reasons:

- New clinical/diagnostic information (e.g. pathology report) suggests a diagnosis other than keloid
- Intolerable local or systemic toxicity from Imiquimod
- Clinical evidence of keloid recurrence. These participants will progress to intralesional steroid injections or excision as per standard of care.
- Any participant who becomes pregnant during the study
- Withdrawal of consent

Subjects who withdraw consent will be withdrawn from the trial. The subjects will be made aware that this will not affect their standard of care. Subjects will be made aware (via the information sheet and consent form) that should they withdraw the data collected will be retained and used as part of the study analysis.

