7.1 Sample Size Determination

In this open-label, single-arm pilot study, 10 patients will be enrolled.

The sample size calculation was based on a historical recurrence rate of 70% at 8 week follow-up after excision alone and an expected 25% recurrence rate with Imiquimod treatment. Using 80 % power and $\alpha = 5\%$, the estimated sample size required is 8. Allowing for a withdrawal rate of approximately 20 %, 10 subjects will have to be enrolled.

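### The analysis has no rule for other keloid treatment given before a declared recurrence, so a co-treated patient who stays clear counts as an imiquimod success against an excision-alone benchmark

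*Combined protocol and SAP*

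**What the plan says.** Section 5.6 sets a limit first: "Concomitant medications/treatment for the keloid lesions should be kept to a minimum during the study". It then makes an exception where the patient's welfare is thought to need it: "they may be given at the discretion of the investigator according to the local standard of care". It adds a recording duty, "The drug, dose and duration should be recorded", and one prohibition: "Immunosuppressive medications including oral corticosteroids are specifically excluded for the duration of this study". Local keloid treatments are not on any prohibited list.

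Section 1.1 says that, often, "surgical excision is combined with adjuvant therapies such as corticosteroids and immunomodulators at the time of skin closure". Section 6.2 has the excision itself done under current standard of care.

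The outcome in Section 2 is a clinical judgement: visits at 2, 4 and 8 weeks and a phone call at 12 weeks, "to assess for clinical evidence of lesion recurrence". Section 7.1 sizes the study on "a historical recurrence rate of 70% at 8 week follow-up after excision alone" and an expected 25% with imiquimod. Section 7.2 reports a response rate with a 95% confidence interval and does not define response. Section 7.3 analyses those who completed the protocol. None of 7.1 to 7.3 mentions concomitant keloid treatment.

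For patients with clinical evidence of recurrence, Section 4.4.1 says: "These participants will progress to intralesional steroid injections or excision as per standard of care". Section 6.4 has the same order: recurrence is judged, then treatment follows.

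**The concern.** The benchmark describes patients who had excision and nothing else. The study patients have excision, imiquimod and, where the investigator sees a need, possibly another keloid treatment. If that other treatment helps keep a site clear, the plan has no step that separates its effect from that of imiquimod. Permitted co-treatment is neither a stopping reason in 4.4.1 nor a protocol breach, so 7.3 does not clearly remove the patient.

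If the other treatment has any benefit, the bias runs towards efficacy. There is no control arm in which the same co-treatment would occur, and the investigator who decides on co-treatment also judges recurrence, unblinded. With 10 patients, one patient is 10 percentage points; with the 8 evaluable patients of 7.1, one is 12.5 points. A choice made after the data are seen about how to classify one co-treated patient could settle the conclusion.

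**Working it through.** **The plan's own figure.** Inputs from 7.1: benchmark recurrence 0.70, expected recurrence 0.25, power 80%, alpha 5% (sidedness not stated; two-sided assumed). The one-sample normal approximation gives

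n = [(1.960 × √(0.70 × 0.30) + 0.842 × √(0.25 × 0.75)) / (0.70 − 0.25)]² = 7.87, rounded up to 8; and 8 / 0.80 = 10.

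Both stated figures reproduce, so the point does not rest on an arithmetic error.

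**A working success rule.** Section 7.2 sets no threshold. A natural reading is that the 95% interval for the proportion clear should exclude the 30% implied by 70% recurrence. Exact (Clopper-Pearson) intervals:

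| Clear / analysed | 95% CI | Excludes 30%? |
|---|---|---|
| 7/10 | 34.8% to 93.3% | yes |
| 6/10 | 26.2% to 87.8% | no |
| 6/8 | 34.9% to 96.8% | yes |
| 5/8 | 24.5% to 91.5% | no |

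With 10 analysed, the rule is 3 or fewer recurrences; with 8, it is 2 or fewer. In both cases reclassifying one patient at the boundary reverses the result.

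**Illustration of the bias.** Assume that imiquimod has no effect (true recurrence 0.70), that all 10 patients are analysed, and that m patients chosen at random are made certain to stay clear by another treatment. The observed recurrences X then follow Binomial(10 − m, 0.70). The false-success probability is P(X ≤ 3), and the expected observed recurrence is 0.70 × (10 − m) / 10.

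| m | P(X ≤ 3) | Expected observed recurrence |
|---|---|---|
| 0 | 1.1% | 70% |
| 1 | 2.5% | 63% |
| 2 | 5.8% | 56% |
| 3 | 12.6% | 49% |

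Each co-treated patient lowers the expected rate by 7 points, not 10, because a randomly chosen patient had a 30% chance of staying clear anyway. A recurrence actually prevented would move the rate by the full 10 points.

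**What the record would support.** Section 5.6 asks for drug, dose and duration, but not body site or start date. Section 4.1 allows any number of keloids, so those fields cannot show whether the study site was treated or whether treatment came before the assessment. Section 6.3 lists new medication and health service use for visits 3 and 4; Sections 6.4 and 6.5 do not list it for visit 5 or the phone call.

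**The case against.** The strongest reply is that 5.6 is a narrow welfare exception, not open permission. It asks for restraint, and no section schedules or expects preventive co-treatment without a declared recurrence. That stands: the exposure may be small, and no frequency is given.

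A reader might infer from 4.4.1 and 6.4 that patients receiving intralesional steroid are being counted as clear. The documents do not support this. Both sections describe treatment after recurrence has been judged, so those patients are already recurrences. Neither section calls the treatment effective, and the Introduction says that keloid therapies all have limited efficacy. The support for co-treatment before recurrence is the account in 1.1 of adjuvants at skin closure.

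A reader might also infer that the plan states that other treatments do not count against the endpoint. It does not. The consequence follows from silence: response is undefined, and no analysis rule mentions the record. One could fairly say that the undefined response is the root defect and this is one result of it. That does not close the gap, since a definition of response that did not address co-treatment would leave it open.

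Finally, counting co-treatment as recurrence makes the endpoint a composite, and in a small sample a treatment given for an unrelated reason moves the rate the other way. Which analysis is primary is partly a matter of preference. Fixing the choice before data are seen is not.

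**Conclusion.** The concern holds in a limited form. Sections 5.6 and 7, followed as written, let a patient who received another keloid treatment before any declared recurrence count as non-recurrent against an excision-alone benchmark. Any effect of that treatment favours imiquimod, and a single-arm, unblinded design cannot offset it.

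The size is unknown. The rise in false-success probability from 1.1% to between 2.5% and 12.6% rests on four assumptions: 70% true recurrence, 10 patients analysed, a success rule that the plan does not state, and 1 to 3 randomly chosen patients made certain to stay clear. It shows how sensitive the result is; to read it as an estimate of bias in this trial would go beyond the documents. The firmer statement is that one patient's classification can decide whether the interval excludes 30%. The plan should be changed before data are analysed.

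**What to change.** Add to 7.2: any other keloid-directed treatment at the study excision site, given before the 8-week assessment and without a previously declared recurrence, counts as recurrence in the primary analysis. Eight weeks is the benchmark time in 7.1. Add one sensitivity analysis on observed clinical status, and list all such use per patient.

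In the case report form, record site and start date alongside drug, dose and duration, and ask about such treatment at visit 5 as well as at visits 3 and 4.

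This is an analysis and recording rule. It leaves the clinical permission in 5.6 and every patient's care as they are.

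The cost is a short SAP addition, a small form change and some conservatism where the treatment was given for another reason. The conservatism is slight if use is as rare as 5.6 intends, but it grows with use. At 8 evaluable patients and a true 75% clear, the chance of 6 or more clear is 67.9%. If 10% of the clear patients were recounted as recurrences, the rate would be 0.75 × 0.90 = 67.5% and the chance 48.9%. The sensitivity analysis on observed status is there to show this.

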5.7 Packaging

5% Imiquimod cream is supplied in single-use packets each of which contains 250mg of the cream, equivalent to 12.5mg of Imiquimod. 5% Imiquimod cream is supplied in a box of 24 packets each (7).

As there is no blinding in this study, the imiquimod will be prescribed in its standard packaging, with additional labelling to comply with regulatory requirements.

5.8 Blinding of Study Drug

The study is not blinded.

5.9 Receiving, Storage, Dispensing and Return

5.9.1 Receipt of Drug Supplies

Upon receipt of the of the study treatment supplies, an inventory must be performed and a drug receipt log filled out and signed by the person accepting the shipment. It is important that the designated study staff counts and verifies that the shipment contains all the items noted in the shipment inventory. Any damaged or unusable study drug in a given shipment will be documented in the study files. The investigator will make a notation of any damaged or unusable study treatments that were supplied to the investigator's site.

5.9.2 Storage

The drug will be stored and handled per the specifications on the package insert. The drug will be stored at 4-25°C (39-77°F) with the temperature being monitored in a secure location contained in an appropriately designated secure area. Avoid freezing. Keep out of reach of children.

5.9.3 Dispensing of Study Drug

The study physician or designee in the dermatology clinic will dispense the medication and keep detailed dispensing records. The physician will write a prescription for the amount of medication to be dispensed.

5.9.4 Return or Destruction of Study Drug

At the completion of the study, subjects will be asked to return all unused medication at the final follow-up visit. There will be a final reconciliation of drug shipped, drug consumed, and drug remaining. This reconciliation will be logged on the drug reconciliation form, signed and dated. Any discrepancies noted will be investigated, resolved, and documented prior to return or destruction of unused study drug. Drug destroyed on site will be documented in the study files.

CONFIDENTIAL

6 Study Procedures

Patients will be recruited through the routine work of the Dermatology departments at the Hospital of the University of Pennsylvania. Recruitment and consent will be obtained by the principle investigator or another Dermatology physician as delegated by the investigator seeing the patient in the outpatient clinic. Patients seen in the outpatient clinic with clinical representation of keloids will be approached by the Dermatology attending as part of clinical evaluation, and written, informed consent will be obtained from the patient prior to any research related procedures are conducted.

It will be explained to the potential participant that entry into the trial is entirely voluntary and that their treatment and care will not be affected by their decision. It will also be explained that they can withdraw at any time. In the event of their withdrawal it will be explained that their data collected so far will be retained and used as part of the study analysis.

	Visit 1 (Week 1)	Visit 2 (Week 2)	Visit 3 (Week 4)	Visit 4 (Week 6)	Visit 5 (Week 10)	Phone encounter (Week 14)
Informed consent	X					
Urine pregnancy test	X					
Imiquimod application	X (start after visit)	X	X	X		
Keloid excision		X				
Excision specimen sent to pathology per SOC		X				
Photograph of lesion	X (optional)	X (optional)	X (optional)	X (optional)	X (optional)	
Evaluation of local site reaction		X	X	X	X	
Evaluation for recurrence			X	X	X	X

6.1 Visit 1

Diagnosis of keloid will be made clinically by a Dermatology attending in the University of Pennsylvania Dermatology outpatient clinic. If the patient meets all inclusion and exclusion criteria set by the study and wishes for the keloid to be surgically removed, the patient will be approached by the Dermatology team for recruitment into the study. The patient will be given the opportunity to have a further discussion about the study and receive answers to any questions they may have. If the patient is agreeable to participating in the study, written and informed consent will be obtained from the patient or the patient's legally authorized representative. A medical history will be taken, demographic data will be collected, and photo-documentation of the lesions will be recorded.

A urine pregnancy test will be conducted prior to receiving study drug, for all female subjects of childbearing potential who are not postmenopausal > 1 year or surgically sterile. Subjects with a positive urine pregnancy test will be excluded from the study. Subjects will be asked to use contraception during treatment period. If

CONFIDENTIAL

indicated, (missed period, unprotected sexual intercourse, or Investigator discretion), a urine pregnancy test may be administered subsequently at the discretion of the Investigator.

A procedure appointment will be made for the surgical keloidectomy, and the subject will be instructed to apply Imiquimod 5% daily Monday to Friday the week prior to the scheduled excision date. The cream should be left in place for approximately 8 hours. The treatment area should include a 1 cm margin of skin around the tumor. The diameter of cream droplet applied should range from 5 mm to 10 mm for keloid areas of 0.5 cm to 5 cm, respectively.

The subject will also continue applying 5% Imiquimod daily as instructed for 5 more weeks after surgery. Subjects will be followed-up in the outpatient clinic at 2, 4, and 8 weeks post-excision and by phone 12 weeks post-excision.

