3.4 Primary Safety Endpoints

To assess the safety and tolerability of 5% Imiquimod in subjects undergoing keloid excision.

At each clinic follow-up visit (2, 4, 8 weeks after excision), the investigator will rate the local site reaction on the following scale:

- None
- Mild reaction (slight redness, discomfort, no swelling, no ulceration)
- Moderate reaction (redness, pain and swelling, no ulceration)
- Severe reaction (redness, pain, swelling, and ulceration)

4 Subject Selection and Withdrawal

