4.1 Inclusion Criteria

1. Age \geq 18
2. Men and women who present clinically with keloids requesting excision
3. Any number of keloids
4. Keloid no larger than 5cm in diameter at the base
5. Clinical findings consistent with keloid formation, including: a scar that does not spontaneously regress, extends beyond borders of normal tissue, may be pruritic, may be painful.
6. Location of keloid in low-risk areas – areas other than above the neck, hands, feet, or groin
7. Able and willing to give informed consent

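### No local site rating is made before the first dose, so a Visit 2 grade may partly reflect the keloid rather than imiquimod

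*Combined protocol and SAP*

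**What the plan says.** The schedule table in section 6 marks "Evaluation of local site reaction" at Visits 2, 3, 4 and 5 and leaves Visit 1 empty. The imiquimod row for Visit 1 reads "X (start after visit", so Visit 1 is the only scheduled visit before any drug. Section 6.1 then has the patient "apply Imiquimod 5% daily Monday to Friday the week prior to the scheduled excision date". For Visit 1 it lists history, demographics, photographs and, where applicable, a pregnancy test, but no site rating.

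The entry criteria (4.1) describe lesions that "may be pruritic, may be painful". The background (1.1) says keloids "can cause pain, burning, itching, and restriction of motion".

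The scale in 3.4, repeated in 6.3, has four levels. Its second level is "Mild reaction (slight redness, discomfort, no swelling, no ulceration" and its third is "Moderate reaction (redness, pain and swelling, no ulceration". Severe adds ulceration. The scale has no item for attribution to drug or lesion.

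The text and the table differ on when the scale is used. Sections 2 and 3.4 place it at 2, 4 and 8 weeks after excision, and 6.2 mentions no rating at Visit 2. The Visit 2 rating therefore exists only as a table entry, with no stated timing relative to the excision.

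**The concern.** Starting imiquimod before excision is what sets this study apart from the published series (1.4, 1.5). If the Visit 2 rating is made before surgery, it is the only scheduled look at local tolerability under drug without a surgical wound. Visits 3 and 4 follow the excision, and Visit 5 comes three weeks after the last planned dose.

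With one arm, the only comparator for Visit 2 is the same patient's site before the first dose, and that is not graded. Pain or discomfort that the patient brought to the study can enter the Visit 2 grade and be read as a drug reaction. A patient who was already symptomatic and got worse on treatment cannot be shown to have worsened on this scale. Safety and tolerability is the stated secondary objective. A pre-drug grade that was not taken cannot be recovered once treatment begins.

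**Working it through.** The plan gives no figure on this point. Its one computed figure, the sample size in 7.1, concerns recurrence. With a one-sample normal approximation (70% against 25%, two-sided 5%, 80% power), [(1.96 × √0.21 + 0.842 × √0.1875) / 0.45]² = 7.87, rounded up to 8, and 8 / (1 − 0.20) = 10. Sidedness is not stated. Nothing below depends on this figure or changes it.

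The check is a comparison of the sections, visit by visit:

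| Visit | Drug | Keloid | Rating in table | Rating in text |
|---|---|---|---|---|
| 1 | none yet | present | no | no (6.1) |
| 2 | after about 1 week | present until excised | yes | no (3.4, 6.2) |
| 3 and 4 (2 and 4 weeks after excision) | continuing | removed | yes | yes (3.4, 6.3) |
| 5 (8 weeks after excision) | ended 3 weeks earlier | removed | yes | yes (3.4, 6.4) |

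1. **Baseline.** No rating on this scale precedes the first dose in either the table or the text.

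2. **Overlap with keloid symptoms.** Pain appears in 1.1, in 4.1 and in the Moderate and Severe grades. Discomfort appears in Mild. Itch is in 1.1 and 4.1 but is not on the scale. Redness is in every grade above None but is not among the keloid features in 1.1 or 4.1. The overlap in the documents therefore runs through pain and discomfort. A painful lesion without redness does not meet Mild as written.

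3. **Other baseline information.** Section 8.1 defines a preexisting condition as one present at the start, and makes it an adverse event if its frequency, intensity or character worsens. Section 8.2 requires questioning about adverse events at each contact. A history is taken at Visit 1. Photographs are to be recorded according to 6.1 but are optional in the table, and they cannot show pain. None of these gives a grade on the scale.

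4. **Size.** One misattributed patient moves a Visit 2 reaction rate by 1/10 = 10 percentage points if 10 are rated. If only the 8 expected after 20% withdrawal are counted, the shift is 1/8 = 12.5 points. The number misattributed cannot be estimated from the documents.

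**The case against.** The strongest reply is that the safety endpoint as worded in 3.4 uses only the visits at 2, 4 and 8 weeks after excision. By then the keloid is gone and the surgical wound is the main confounder, which a Visit 1 rating would not address. This stands. The point concerns only the Visit 2 rating, which the table requires and the text omits.

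A reader might infer that drug and lesion effects cannot be told apart at all, or that worsening would go unrecorded. The documents do not support that. Treatment extends to a 1 cm margin of skin around the keloid (5.2, 6.1), and a dermatologist can see a reaction there. The rule in 8.1 captures worsening of a preexisting condition, and its definition of such a condition carries no threshold of clinical significance; that qualifier belongs to physical examination findings. What remains is narrower: the scale gives one overall grade, does not separate margin from lesion, and has no pre-drug value.

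A reader might also assume a rate of symptoms at entry and multiply by ten. An assumed 20% to 60%, for example, would give 2 to 6 of 10 patients graded at least Mild without any drug effect. That only restates the assumption, and it overlooks that every grade above None also lists redness.

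Finally, no stated decision turns on the Visit 2 grade. Section 7.2 treats endpoints other than response descriptively, and the dose-adjustment algorithm in 5.2 refers to the later and unscheduled visits. This is fair, and it keeps the point minor.

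**Conclusion.** The point holds in limited form, as a cheap improvement. The first rating on the local site scale comes after about a week of drug, no grade precedes it, and there is no control arm. A Visit 2 grade may therefore contain discomfort or pain from the keloid, and change under pre-treatment cannot be shown on this scale. Ungraded baseline information does exist.

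The size is unknown beyond the 10 to 12.5 percentage points per misattributed patient. The importance given to Visit 2 assumes that its rating is made before excision, which is a reasonable reading but is nowhere stated. The recurrence endpoint, the sample size and the ratings after excision are unaffected.

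**What to change.** - Mark the local site rating at Visit 1 in the schedule table and add it to 6.1, made before the first application on the scale in 3.4.
- State that the Visit 2 rating is made before excision, and reconcile the table with 3.4 and 6.2, which omit it.
- Report the Visit 2 grade alongside its change from Visit 1.
- Confine that change to Visit 2. After excision the keloid has been removed, and subtracting its entry symptoms could hide true reactions.

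The dermatologist already examines the lesion at Visit 1 to make the diagnosis, so the cost is one table cell, one CRF line and about a minute per patient. Enrolment numbers and treatment do not change.
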